Building Mobile HIV Prevention and Mental Health Support in Low-resource Settings

NCT06229132 2/15/2025

BACKGROUND

In July 2021, the study team received a supplement to the R01 grant to enroll a small sample (N=45) of transgender and gender-diverse (TGD) Romanians in addition to the original sample of 800 GBM. This decision is based on the following rationale. TGD individuals remain a hidden group in the Central Eastern European (CEE) country of Romania, with few protections, few equal rights, and many unmet needs. Emerging research with TGD persons in the region indicates that TGD Romanians report particularly high rates of depression, HIV, and hazardous alcohol use, primarily driven by the country's high structural stigma. Romania's healthcare system has little expertise for addressing these syndemic health threats. No targeted needs assessments or interventions exist to date in order to remedy these adversities and promote the wellbeing of TGD in Romania, or anywhere in CEE – the region with the fastest-growing HIV epidemic in the world. In response, we proposed to create and pilot-test the first intervention in CEE to address the mental, sexual, and behavioral health of TGD people. Compared to the GBM sample, however, TGD participants in formative work indicated that a mental health focus, rather than a sexual or behavioral health focus (while still addressing these as relevant to each participant) should be adopted. As a result, our EQuIP (Empowering Queer Identities in Psychotherapy) intervention is being delivered in this supplement to the TGD sample of 25 participants.

In Aim 1, we will identify unique needs of TGD Romanians via focus groups. Findings will be used in Aim 2 to modify the intervention manual to address gender minority stress and other TGD-specific determinants of mental health, hazardous alcohol use, and HIV risk. In Aim 3, we will evaluate the adapted intervention's feasibility, acceptability, and efficacy potential in a one-arm trial with 25 TGD Romanians.

Research Aims & Abstracts

The aim of this study is to evaluate the intervention's feasibility, acceptability and efficacy potential in a one-arm trial with 25 TGD Romanians. Participants will receive 16 weekly mHealth sessions hypothesized to reduce depression, anxiety, HIV risk, and hazardous alcohol use; outcome data will be collected at baseline and 5-month follow-up.

Scientific Abstract

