Transgender and gender diverse (e.g., gender non-binary) (TGD) individuals remain a hidden group in the Central Eastern European (CEE) country of Romania, with few protections, few equal rights, and many unmet needs. Emerging research with TGD persons in the region indicates that TGD Romanians report particularly high rates of depression, anxiety, HIV, and hazardous alcohol use, primarily driven by the country's high structural stigma. Romania's healthcare system has little expertise for addressing these syndemic health threats. No targeted needs assessments or interventions exist to date in order to remedy these adversities and promote the wellbeing of TGD in Romania, or anywhere in CEE – the region with the fastest-growing HIV epidemic in the world. In response, we propose to create and pilot-test the first intervention in CEE to address the mental, sexual, and behavioral health of TGD people. EQuIP, MPI [name]'s intervention, was tested with various populations in the US and in China. The first pilot study tested successfully the efficacy of a minority-stress-focused cognitive—behavioral therapy (CBT) intended to improve mental and behavioral health for sexual minority women. This treatment was adapted for the present research based on local Romanian TGD needs uncovered in the first part of this pilot study (which ended in 2021). The adaptation was guided by the gender minority stress framework that acknowledges unique TGD stressors, whose impact the intervention intends to modify. As such, the intervention consists of 16 1-hour sessions delivered by trained therapists on Zoom. The team will evaluate the new intervention's feasibility and acceptability in a one-arm trial with 25 TGD Romanians. Data will be collected at baseline and 5-month follow-up.

STUDY DESIGN

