Feasibility and acceptability measures and analyses. Feasibility will be assessed by: 1) examining screener data for eligibility ratio and reasons for enrollment refusal; and 2) participants' rating of participation ease, including in using the mobile platform, and counselors' rating of intervention delivery ease (mean score of ³4 on a scale of 1-5 indicates high feasibility). Acceptability will be assessed by: 1) tracking # of sessions completed, with a minimum session completion dose by ³80% of participants (which is ³10 sessions, completed by 86% of participants); and 2) post-intervention ratings (mean score of ³4 on a scale of 1-5 indicates high acceptability) of the: a) usefulness of intervention content and perception of personal progress, b) intervention structure, c) delivery modality, d) counselor expertise, and e) therapeutic alliance including trust and comfort. Finally, exit interviews with all participants and counselors will qualitatively assess intervention accessibility and participation comfort, content relevance and TGD-sensitivity, perceived impact on health and wellbeing, duration, and if participants would recommend it to friends (compensated with the Romanian equivalent of \$30).

Intervention outcomes. This pilot will establish effect sizes necessary to power a future larger trial for our main outcomes: depression, anxiety, HIV risk, and hazardous alcohol use.

Analyses for intervention evaluation. Findings will allow us to assess the intervention's potential impact on mental health, HIV risk, hazardous drinking, and psychosocial mechanisms theorized to underlie the adverse impact of gender minority stressors on participants' health. Outcome distributional properties will be examined using standard summary statistics (means, SDs, medians, skew, kurtosis) and graphical summaries (boxplots, density plots). For continuous or discrete variables with skewed distributions (e.g., hazardous drinking frequency), we will investigate transformation to symmetry (e.g., log and square root). Given the small sample size (n = 25), we will not have sufficient power to use traditional statistical significance testing. However, in order to gather preliminary data on the magnitude of the intervention's possible impact on each outcome, we will conduct paired-sample t-tests to assess pre-post intervention change (from baseline to immediately post-intervention 5 months later).

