Power. Utilizing the t-tests results, we will calculate Cohen's d as a measure of effect size and interpret effects as small (d = 0.2), medium (d = 0.5), and large (d = 0.8) following published guidelines.

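### Does the pilot need a missing-data rule for participants without 5-month outcomes or ratings?

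*Combined protocol and SAP*

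**What the plan says.** Research Aims & Abstracts gives two assessment times: "outcome data will be collected at baseline and 5-month follow-up". The Scientific Abstract repeats this: "Data will be collected at baseline and 5-month follow-up". Neither statement restricts follow-up to people who complete the sessions.

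Under Analyses for intervention evaluation the outcome analysis is a paired comparison: "we will conduct paired-sample t-tests to assess pre-post intervention change (from baseline to immediately post-intervention 5 months later"). Under Power, the effect size comes from the same tests: "Utilizing the t-tests results, we will calculate Cohen's d as a measure of effect size". Intervention outcomes gives the purpose: "This pilot will establish effect sizes necessary to power a future larger trial for our main outcomes". The analysis section also limits what it claims: "Given the small sample size (n = 25), we will not have sufficient power to use traditional statistical significance testing".

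Acceptability is judged partly on "post-intervention ratings (mean score of ³4 on a scale of 1-5 indicates high acceptability"), where the superscript 3 is evidently a converted 'at least' sign. The same section plans that "exit interviews with all participants and counselors will qualitatively assess intervention accessibility and participation comfort".

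The documents give no missing-data rule, analysis set, imputation, sensitivity analysis or expected loss rate. The only figures near the subject are the session-completion criterion (80% of participants) and the 86% in brackets beside it. Both concern sessions attended, not outcomes collected.

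**The concern.** A paired t-test needs both values. With a single post-baseline assessment there is no interim value to draw on, so a person without a 5-month score contributes nothing to d. With one arm there is no control group in which similar loss might offset the effect, so selective loss passes straight into d. A confidence interval shows sampling error and does not reveal it.

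The d values are meant to inform the size of a later trial. Required sample size varies roughly as 1/d², so an inflated d would leave that trial too small and a deflated d would make it too large. The ratings raise the same question: a mean of at least 4 among those who answered need not hold for everyone enrolled. The session criterion can be met with 5 of 25 below the minimum dose (80% of 25 is 20), so appreciable drop-off is compatible with declared success, although that is not a forecast of missing outcomes.

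**Working it through.** The plan contains no sample-size or attrition calculation to reproduce. From the documents: n = 25, one arm, two assessments, benchmarks for d of 0.2, 0.5 and 0.8, and a rating threshold of 4 on a 1-5 scale. Everything else below is an assumption for illustration.

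**1. How far can completers' d move?** Assume SD 1 at each time, pre-post correlation 0.6 and mean improvement 0.5. The SD of change is √(2 × (1 − 0.6)) = √0.8 = 0.894, so true d = 0.5/0.894 = 0.559. I simulated 40,000 trials of 25 per setting. Loss was logistic in the named driver, with slope 0.5 (mild) to 1.5 (strongest) per SD of the driver. Entries are median completer d.

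| Assumed loss | Non-improvers leave, mild / strongest | Improvers leave, mild / strongest | Sampling SD of d |
|---|---|---|---|
| 8% | 0.61 / 0.70 | 0.53 / 0.49 | 0.24 |
| 12% | 0.63 / 0.76 | 0.51 / 0.45 | 0.24-0.25 |
| 20% | 0.68 / 0.88 | 0.48 / 0.37 | 0.25-0.27 |

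If loss depends on baseline severity, the 20% range is 0.47 to 0.68. At 8% to 12% loss with mild selection, the largest shift is 0.631 − 0.559 = 0.072 and the smallest is 0.559 − 0.531 = 0.028. Even the largest is under a third of the sampling SD.

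The chance that d reaches 0.8 is about 0.15 with no loss. At 20% loss it is 0.63 or 0.06 with the strongest selection, but 0.32 or 0.11 with mild selection. At 8% loss and mild selection it is 0.22 or 0.13.

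**2. The same question from the observed side.** Suppose completers show d = 0.50 with SD of change 1, a share q is missing, and the missing have mean change m. Then d for all = [(1 − q) × 0.5 + q × m] / √(1 + q(1 − q)(m − 0.5)²). With 5 of 25 missing (q = 0.2):

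- m = −0.5: 0.30/√1.16 = 0.28
- m = 0: 0.40/√1.04 = 0.39
- m = 1: 0.60/√1.04 = 0.59

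The error can go either way. For comparison, the approximate 95% half-width for d = 0.5 with all 25 present is 1.96 × √(1/25 + 0.25/50) = 0.42.

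**3. Would a different method repair it?** A two-wave likelihood estimate using every baseline was computed on the same simulated data, at 20% loss (true d 0.56):

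- Loss depends on baseline: 0.55 to 0.56, against 0.47 to 0.68 for the t-test. It works.
- Non-improvers leave, strongest selection: about 0.82, against 0.88. Most of the error remains.
- Severe at 5 months leave, strongest selection: about 0.73, against 0.68. It is further off.

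Setting missing values to no change gives 0.58 to 0.73 if non-improvers leave and 0.33 to 0.42 if improvers leave, so it is not reliably cautious. A baseline comparison of 20 retained with 5 lost has standard error √(1/20 + 1/5) = 0.5 SD, too coarse to show which mechanism operated.

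**4. Ratings.** With r people rated at mean s, the mean for all 25 falls below 4 if the unrated would average less than (100 − r × s)/(25 − r).

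- r = 20, s = 4.2: (100 − 84)/5 = 3.2
- r = 22, s = 4.2: (100 − 92.4)/3 = 2.53
- r = 20, s = 4.75: (100 − 95)/5 = 1.0, the bottom of the scale
- r = 22, s = 4.5: (100 − 99)/3 = 0.33, which is impossible

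The verdict can turn on the unrated only when the observed mean is close to 4.

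**The case for a change.** The strongest case for a change is that the omission is genuine and bears on the purpose the plan states for itself. A later planner who reads d without knowing how many pairs produced it cannot judge it. At 20% loss and strong selection, a d of 0.88 in place of 0.56 would give about 40% of the needed sample, since (0.56/0.88)² = 0.40. A d of 0.37 would give about 2.3 times it, since (0.56/0.37)² = 2.29. A few sentences in the plan would cost almost nothing, and an intention to hold qualitative exit interviews with everyone is not a rule for missing scores.

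Part of this stands. The estimate is a completer estimate, and a reader needs the number of pairs and the number rated out of those enrolled. But those counts come with any competent report of a 25-person study, and a paired t-test displays its own n. The large distortions need both an assumed 20% loss and the strongest selection simulated, and nothing in the documents supports either.

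The ratings argument is weaker. The items cover counselor expertise, therapeutic alliance and personal progress, on which someone who attended few sessions may have little to say. A mean over everyone enrolled is therefore not clearly the right target. Non-attendance already counts through the session criterion, whose data can be tracked for all enrolled.

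**Conclusion.** The plan is silent on missing outcomes, but it need not change. Its stated intention is 5-month data without restriction to session completers, plus exit contact with all participants. What remains is a contingency that analysts would handle by reporting the pairs and ratings obtained and describing d as a completer estimate.

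At 8% to 12% loss with mild selection the shift in d is about 0.03 to 0.07, small beside a sampling SD of about 0.24 to 0.25. It becomes large only at assumed extremes, with a direction the documents cannot settle. These sizes rest on an assumed correlation of 0.6, a true change of 0.5 SD, d defined on the SD of change, and assumed loss rates; with complete follow-up the issue vanishes.

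No analysis examined gives a dependable gain, since each helps under one loss mechanism and misleads under another. Everyone is also enrolled on a high symptom score and there is no control arm. Even with no loss, d would mix treatment effect with regression to the mean and natural course. In a pilot that calls its results preliminary, a formal missing-data strategy is a matter of preference.

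### Cohen's d from at most 25 pairs is planned with no small-sample correction or confidence interval, although it is meant to help power a larger trial; if d is the paired d, the average inflation is about 3%

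*Combined protocol and SAP*

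**What the plan says.** All references are to the combined protocol and SAP, section STATISTICAL ANALYSIS, unless noted.

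- **Purpose (Intervention outcomes):** "This pilot will establish effect sizes necessary to power a future larger trial for our main outcomes". The outcomes listed are depression, anxiety, HIV risk and hazardous alcohol use.
- **Test (Analyses for intervention evaluation):** "Given the small sample size (n = 25), we will not have sufficient power to use traditional statistical significance testing". To gauge the size of possible change, the plan adds that "we will conduct paired-sample t-tests to assess pre-post intervention change".
- **Estimator (Power):** from the results of those t-tests the team will "calculate Cohen's d as a measure of effect size", and the team will "interpret effects as small (d = 0.2), medium (d = 0.5), and large (d = 0.8) following published guidelines".
- **Data (Research Aims & Abstracts):** "outcome data will be collected at baseline and 5-month follow-up". No dropout figure is given.

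The plan does not state which SD divides the mean change. It mentions neither a small-sample correction nor a confidence interval for d. That d will be uncorrected is therefore inferred from silence.

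**The concern.** The plan itself sets significance testing aside as underpowered, so d is the main quantitative result for each outcome. In small samples the expected value of Cohen's d lies further from zero than the true standardised effect, because the reciprocal of a sample SD exceeds, on average, the reciprocal of the true SD. The error is systematic and has a known multiplier.

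Required sample size varies with 1/d squared, so an inflated d used in planning makes the next trial too small. Without a confidence interval, the person planning that trial also sees a single number with no indication of how loosely 25 pairs determine it.

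**Working it through.** The plan contains no power or sample-size calculation, so there is no figure of its own to reproduce.

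**Inputs.** From the plan: 25 participants, paired t-test, Cohen's d, benchmarks 0.2/0.5/0.8. Assumed: d is the paired d, t/√n; differences are normal; 20 completed pairs (20% loss) as a lower case; for the planning illustration only, a two-arm trial, two-sided 0.05, 80% power.

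**1. Average inflation of the paired d.** With m = pairs − 1, E[d] = δ/J(m), where J(m) = Γ(m/2) / [√(m/2) · Γ((m−1)/2)].

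| Pairs | m | J(m) | Inflation, 1/J − 1 | Mean d if true value is 0.50 |
|---|---|---|---|---|
| 25 | 24 | 0.9684 | 3.3% | 0.516 |
| 20 | 19 | 0.9599 | 4.2% | 0.521 |

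The approximation 1 − 3/(4m − 1) gives 0.9684 and 0.9600. Simulation with 400,000 replicates agrees (3.2 to 3.4% at 25 pairs; 4.2 to 4.5% at 20).

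**2. Dependence on the divisor.** Dividing by the baseline SD gives nearly the same inflation as the paired d. Dividing by the pooled pre/post SD gives less: simulation at 25 pairs gave 1.6 to 2.3% for pre-post correlations of 0 to 0.7, so about 1 to 2.5% is a fair range. Applying 0.968 to that version would over-correct: 1.016 × 0.968 = 0.98 and 1.023 × 0.968 = 0.99.

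**3. Size beside random error.** At true d = 0.5 and 25 pairs, the sampling SD of the paired d is about 0.22. The bias of 0.016 is 0.016/0.22, about 7% of one SD. The noncentral-t 95% CI around an observed 0.5 runs from 0.08 to 0.91 (25 pairs) or 0.03 to 0.96 (20 pairs).

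**4. Mean against median (true d = 0.5, 25 pairs).** The uncorrected d falls below the truth in 49% of pilots. Its median is 0.505; the median of the corrected g is 0.489. The correction lowers root mean squared error from 0.224 to 0.216.

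**5. Downstream scale only.** Suppose a true between-arm d of 0.5, for which a two-sample t-test needs 64 per arm. Planning on the mean inflated value gives 60 per arm (0.516) or 59 per arm (0.521), with actual power 77.5% or 76.8%. This shows what a 3 to 4% error in d does; it does not license putting a one-arm d into a two-arm formula.

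**6. What the divisor alone can do.** The paired d equals the raw-SD d divided by √[2(1 − r)]. For r = 0.3, 0.5 and 0.7 the ratio is 0.85, 1.00 and 1.29, a far larger swing than the small-sample bias.

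**The case against.** The best case against acting is that the bias is a property of the mean, while a pilot yields one estimate. The median uncorrected d (0.505) is closer to a true 0.5 than the median g (0.489), and the whole shift is lost inside an interval from 0.08 to 0.91. Cohen's d is a recognised estimator and naming it is no error. On a scale of 0.2/0.5/0.8, the difference between 0.50 and 0.484 changes no interpretation. Skewed outcomes, which the plan expects for drinking frequency, may not follow the normal-theory factor.

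Most of this stands, and it keeps the point small. It also rules out two readings that a reader might infer. One is that every reported d will be too large: about half of single estimates will be too small. The other is that the next trial will be short by about twice the percentage bias. That follows only if the planner happens to see a d equal to its expectation. Over simulated pilots of 25 pairs, the planned size per arm ranges from about 25 to 267 (10th to 90th percentile), with an uncorrected median close to the 64 required.

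The objection does not remove the case for correction. Wide random error does not cancel a mean bias that a known factor removes. The corrected value has the lower mean squared error and, averaged over simulated pilots, raises the future trial's expected power by about 1.7 points (75.6% to 77.3%). A confidence interval is needed in either case.

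**Conclusion.** The point holds as a minor improvement. The planned estimator, read as the paired d with roughly normal differences, is inflated on average by 3.3% at 25 pairs. The 4.2% figure rests on an assumed 20 completers. With a pooled pre/post SD the inflation at 25 pairs is about 1 to 2.5%, and the plan does not say which divisor applies. In every case it is small beside a sampling SD of about 0.22.

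A reader might also infer that the pilot exists only to supply effect sizes, so that this bias undermines it. The documents do not support that: the Research Aims name feasibility, acceptability and "efficacy potential in a one-arm trial with 25 TGD Romanians", and powering a later trial is one stated use. Nor do they say that the later trial has two arms.

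The unstated divisor, the imprecision, and the use of an uncontrolled pre-post change as if it were a treatment contrast all matter more to planning than the 3%.

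**What to change.** Amend the Power paragraph to do four things:

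1. Name the SD that divides the mean change.
2. Report the small-sample-corrected effect size (Hedges g) for each outcome, with the factor matched to that divisor and to the completed pairs. For the paired d it is J(n − 1), which is 0.968 at 25 pairs.
3. Give a 95% CI with each effect size.
4. Carry the corrected value and its interval into planning of the larger trial, and state that a one-arm pre-post effect is not a between-arm effect. Reporting the pre-post correlation and both SDs would let planners convert between scales.

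The cost is SAP wording and one multiplication plus one interval per outcome; no new data or design change is needed. Reported effects become slightly smaller, and the median estimate sits slightly below the true value (0.489 for a true 0.5 at 25 pairs).
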